4.1 General

All patient data collected during the study will be listed by patient and site.

Appropriate descriptive statistics will be produced by treatment arms according to the nature of the variable.

- For continuous data, number of observations, mean, standard deviation, median, first (Q1) and third (Q3) quartiles, range (minimum and maximum) will be presented; 95% confidence intervals will be presented, where applicable.
- For categorical data, frequency distributions and percentages will be presented; 95% confidence intervals (Wilson method with continuity correction) per category will be presented, where applicable. Where applicable (and if not otherwise stated), treatments will be compared by means of Fisher's exact test or Chi-squared, depending on data distribution (i.e., deciding for Fisher test if there are cells with expected count less than 5).
- For time-to-event variables, cumulative freedom from event will be evaluated using the Kaplan-Meier method. The degree of uncertainty will be expressed with 95% confidence limits (calculated per the method proposed by Greenwood [4]). Comparison of curves among arms will be performed with the log-rank test. Kaplan-Meier graphs will be presented along with the number of patient-at-risk at exact timepoints. Subjects who are free from event will be censored at the last available date. An additional analysis for time to death will be performed, where specific reasons for discontinuation will be incorporated into the analysis for determining censoring and failure status. Specifically, study discontinuation for Adverse Event or, Death or, Loss to follow-up will be considered as failure events. Subjects who have discontinued for other reasons without an event will be censored at the date of discontinuation.

Standard/Forms/Template				
Title		Statistical Analysis Plan Template		
Code		Version	Effective Date	Page
PPD		01	29 Aug 2022	24 of 78

Unless otherwise specified, the significance level used for other statistical testing (for descriptive purposes) will be 0.05 and two-sided tests will be used.

For the two co-primary endpoints, normality assumptions will be checked through visual inspection and statistical tests (Shapiro-Wilk's test). The following scenario can be expected:

- normality assumptions are met with both checks, only data using original scales will be analyzed by the parametric test;
- normality assumptions are not met on at least one of the two checks: data will be presented in the original and also in the transformed scales by using parametric tests (as supplementary analysis). In the table on log-transformed scale, the back-transformed treatment estimate will be provided for interpretation purposes. In case normality is not met on the original scale and it is not met also on the log-transformed scale, the analysis will be performed on the original scale only.

Visual inspection is intended as the visual evaluation of the histogram, and the normal quantile-quantile plot (Q-Q) plot of the observed values of the variable of interest (section 7.1.1.1 and 7.1.1.2 provide more details).

- For the histogram, normality is assessed if the histogram of the data mimics a normal distribution (bell-shaped histogram).
- For the Q-Q plot, it is constructed by plotting the empirical quantiles of the data against corresponding quantiles of the normal distribution. If the empirical distribution of the data is approximately normal, the quantiles of the data will closely match the normal quantiles, and the points on the plot will fall near the line $y=x$.

Normality checks (based on visual inspection and statistical tests) are to be performed on observed data and – in case normality on observed data is not met - also on logarithmic scale. Normality will be checked at the Blind Data Review Meeting.

Graphs used for the visual inspection and the statistical tests will be saved as SAS outputs in PDF and delivered together with the TLF package as supplementary material.

The visual inspection and the statistical test for the normality assumption of the ANOVA model for the co-primary endpoints are intended for:

- the primary analysis
- supplementary analysis (PP set).

In case normality is not met, log-transformed data will be used for :

- the primary analysis
- supplementary analyses (complete case and PP set)
- Sensitivity analysis (MAR).

Standard/Forms/Template				
Title		Statistical Analysis Plan Template		
Code		Version	Effective Date	Page
PPD		01	29 Aug 2022	25 of 78

For all other analyses (e.g., secondary efficacy endpoints), normality assumptions will only be checked through the statistical test (Shapiro-Wilk's test). If the normality assumption is not fulfilled data will be presented in the original scale and analyzed by both parametric and non-parametric tests.

In case data transformation is needed to meet normality assumptions, a specific focus will be added in CSR for interpreting the fact that the comparison between treatments is based on the transformed scale. A similar approach will be followed in case of use of non-parametric tests. Interpretation of potential discordant results between analyses performed on original and transformed scales (or analysis on original scale tested using parametric and non-parametric methods) will also be provided in the CSR.

Additional post-hoc analysis may be produced according to the results obtained. Any deviations from the original statistical plan (including unplanned analyses) will be documented in the CSR.

4.2 Analysis sets

4.2.1 Screened set

The Screened set will consist of all patients with signed written informed consent.

4.2.2 Enrolled set (ENR)

The ENR set will consist of all patients with signed written informed consent and fulfillment of eligibility criteria (i.e., not reported as screening failure).

4.2.3 Randomized set (RND)

The RND set will consist of all patients in the ENR set who are randomized to the study, regardless of whether they receive the IMP or not. The RND population will be used for the primary analysis of the study (including the Analysis of primary endpoint as described in Section Analysis of primary endpoint7.1 and Table 2).

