4. SELECTION OF STUDY POPULATION

Number of patients: approximately 66 adult patients hospitalized with ARDS will be enrolled to target 60 evaluable patients. A patient is considered enrolled if, after signature of consent and screening, it is determined that (s)he fully meets all the Inclusion Criteria and none of the Exclusion Criteria described in Sections 4.1. and 4.2. below.

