4.2.4 Full Analysis set (FAS)

The FAS population will consist of all randomized patients who received at least one dose of the investigational product. FAS population will be analyzed according to intention-to-treat (ITT) principle, i.e., by treatment allocation regardless happening of intercurrent events. The FAS population will be used for the supplementary analyses of the primary analysis of the study and to present results on secondary efficacy data.

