5.2 Protocol violations

All the protocol deviations will be discussed case by case before unblinding of the treatment code, with the clinical team during the BDRM and described in the BDRM Report.

Number of occurrences and of subjects with at least one major, minor, and protocol deviation impacting on the analysis of primary endpoints that lead to exclusion from PP set will be summarized for each treatment and overall. Further details on PD management and classification are provided in the Protocol Deviation Management Plan and relevant documentation.

As an example, a non-exhaustive list of Protocol Deviations leading to exclusion from the PP set can be the following:

- Inclusion of the patient in the study in violation of inclusion/exclusion criteria
- Intake of prohibited medications

Standard/Forms/Template				
Title		Statistical Analysis Plan Template		
Code		Version	Effective Date	Page
PPD		01	29 Aug 2022	35 of 78

- Poor compliance with IMP
- Missing of assessments for the primary endpoint

Protocol deviations will be listed as well using the randomized set.

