11.1 Derivations and date conventions

11.1.1 Variable derivation

Table 3: Variable derivation rules

Parameter	Calculation
Screened	A patient is considered screened if (s)he has “Date of Written Informed Consent Signature” filled
Screening failure	A patient is considered screening failure if (s)he when “Did the subject complete the study?” is answered “No” on the End of Study Form and Primary reason for study discontinuation = “Screening Failure”
Enrolled	A patient is considered enrolled if (s)he has been screened and (s)he is not a screening failure.
Treatment completed/discontinued	A patient is considered as a treatment completer when : Primary reason for end of treatment is = “Treatment completed” or [Primary reason for end of treatment is = “IMP Discontinuation Criteria” and the criteria specified is = “The patient is discharged home”]. Otherwise, the patient is considered as Treatment discontinued
Change from baseline	Each change from baseline will be defined as difference between the value (minuend) at each post-baseline assessment and the baseline value (subtrahend).
Patient with past disease (medical history)	A patient is considered with past disease if CRF term “Has the patient experienced any past and/or concomitant diseases or past surgeries?” = YES and at least a medical history term has “Ongoing” not flagged. Otherwise the patient is considered as with no past diseases.
Patient with concomitant disease	A patient is considered with concomitant disease if CRF term “Has the patient experienced any past and/or concomitant diseases or past surgeries?” = YES and at least a medical history term has “Ongoing” flagged. Otherwise the patient is considered as with no concomitant disease.
Time from randomization to study discontinuation (days)	End of Study date – Randomization date + 1
Length of study (days)	Last available date – Randomization date + 1

Standard/Forms/Template				
Title		Statistical Analysis Plan Template		
Code		Version	Effective Date	Page
PPD		01	29 Aug 2022	58 of 78

Parameter	Calculation

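### The SAP's randomized set, on which both co-primary endpoints are analysed, can lose a randomized patient whose End of Study reason is recorded as screening failure

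*SAP*

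**What the plan says.** Three definitions in the SAP act together.

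- Section 4.2.3 defines the primary set: "The RND set will consist of all patients in the ENR set who are randomized to the study", whether or not they receive study drug. It adds: "The RND population will be used for the primary analysis of the study". Section 4.11 explains that the primary analysis was moved to this set at the request of a regulatory authority. The protocol (9.4) had used the full analysis set (FAS).
- Section 4.2.2 defines ENR by "signed written informed consent and fulfillment of eligibility criteria (i.e., not reported as screening failure").
- Section 11.1.1 turns this into a rule: "A patient is considered enrolled if (s)he has been screened and (s)he is not a screening failure". The same table identifies a screening failure from the End of Study form, where the patient did not complete the study and the primary reason for discontinuation is screening failure. It sets no condition on timing relative to randomization.

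The other sets are built differently. Section 4.2.4 states: "The FAS population will consist of all randomized patients who received at least one dose of the investigational product". The safety set (SAF, 4.2.5) is worded the same way. Neither refers to ENR.

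**The concern.** A set presented as all randomized patients should depend only on the act of randomization. Here it also depends on a closing reason. For a randomized patient, the site enters that reason after allocation. If the reason is screening failure, the rule as written takes the patient out of both co-primary analyses.

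The patients most exposed are those randomized and then not dosed. They are the patients that RND adds to FAS, and so the ones the regulator's request brings back in. SAP 3.2.2 notes that screening, randomization and the first dose may fall on one calendar day, so a site might treat a patient who never starts treatment as a failed screen.

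At stake is whether the report can say that the primary analysis includes every randomized patient.

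**Working it through.** The point rests on definitions, so the check is to follow each kind of randomized patient through SAP 4.2.2 to 4.2.5 and 11.1.1.

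| Randomized patient | ENR | RND | FAS and SAF |
|---|---|---|---|
| Dosed, not coded screening failure | in | in | in |
| Dosed, later found ineligible, not so coded | in | in | in |
| Not dosed, not so coded | in | in | out |
| Not dosed, coded screening failure | out | out | out |
| Dosed, coded screening failure | out | out | in |

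**Rows 2 and 3** behave as intended. Row 2 shows that ineligibility by itself has no effect. The gloss in 4.2.2 and the rule in 11.1.1 reduce eligibility to the absence of the code. Section 5.2 agrees: it gives "Inclusion of the patient in the study in violation of inclusion/exclusion criteria" as an example of a deviation that excludes a patient from the per-protocol set, which is drawn from FAS. Such patients are expected in the wider sets.

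**Row 4** is the patient whom 4.2.3 means to keep by including the untreated. The code removes that patient from every analysis set except the screened set.

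**Row 5** breaks the nesting. FAS is the supplementary set and should lie inside RND, but this patient is in FAS and not in RND.

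**Disposition.** In SAP 5.1 the only reasons for exclusion from RND are those recorded when the patient was not randomized. Rows 4 and 5 were randomized, so the disposition table cannot account for them. Under 4.3, listings default to RND, so these patients would also be missing from any listing on that default.

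**Planned figures.** The enrolment target reproduces: 60 × 1.10 = 66 (60/0.90 gives 67). Loss of precision is not the issue. The one-sided 95% half-width in SD units is t(0.95, N − 2) × √(1/n₁ + 1/n₂).

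- 33 and 33 patients: 0.411
- 30 and 33 patients (three removed from one arm, an assumed number): 0.421

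Both lie below the plan's stated ceiling of 0.465.

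**The case against.** The strongest reply is that the protocol treats screening failure as a status settled before randomization. Section 6.1.1 assesses eligibility once all screening values are available and records failures at that point. Section 4 counts a patient as enrolled only when, after consent and screening, "it is determined that (s)he fully meets all the Inclusion Criteria and none of the Exclusion Criteria". Section 6.1.2 has eligibility confirmed and then randomization. Section 6.2.1 wants every randomized patient kept and followed. On this view, a randomized patient closed as a screening failure is a site error that the SAP neither asks for nor expects.

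Two further points support the reply. Protocol 11.1 requires an eCRF for every consented patient, so the End of Study form also closes true screen failures; finding the code there does not show that it is used after randomization. Protocol 11.2 provides for programmed edit checks under a validation plan that is not among the documents, and these may already block the combination.

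Most of this stands. It makes the route uncommon, and together with SAP 5.1 and 5.2 it shows that RND was meant to be all randomized patients. It does not supply the missing rule. No text says that a randomization number overrides the code, and the programmed definition in 11.1.1 would act on the code.

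A reader might infer two stronger things that the documents do not support. One is that any randomized patient later found ineligible leaves RND; row 2 of the table shows otherwise. The other is that going onto ECMO after randomization would make a patient a screening failure. The exclusion criterion concerns patients already receiving ECMO, and ECMO by day 14 is a secondary endpoint.

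**Conclusion.** The definition has a gap. As written, a randomized patient with a screening-failure closing reason is excluded from the primary set, in conflict with SAP 4.2.4, 5.1 and 5.2 and with the purpose stated in 4.11. The conclusion assumes that 11.1.1 is programmed literally and that no edit check prevents the combination.

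No size can be put on the effect. The documents do not say how many patients are affected, and there may be none. Under double blinding there is no reason to expect a systematic difference between arms.

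It is tempting to remove a few patients with zero ventilator-free days from one arm and report the shift in its mean. That would not follow the SAP's own derivation. Section 11.1.1 assigns zero to patients who die by day 28 or are never extubated. A patient alive but followed for less than 26 days has the endpoint set to missing, and 7.1.1.2 then imputes it. An untreated patient closed early is not shown to meet either rule for zero.

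This is therefore a low-probability fault in the wording of the primary set. It is worth correcting because the set was adopted to go beyond treated patients.

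**What to change.** 1. In SAP 4.2.3, define RND as all patients with a randomization number, regardless of ENR status, eligibility, End of Study code or treatment received.
2. In SAP 4.2.2 and 11.1.1, limit screening failure to patients who were never randomized, so that every randomized patient is in ENR.
3. At the blinded data review meeting, list any randomized patient with this closing reason and record the outcome in its report. SAP 4.12 places that meeting before database lock.

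The cost is a few sentences and one query. The enrolment target and stated precision do not change. No eCRF completion note is needed: SAP Final 2.0 is dated 30 July 2025 and the protocol planned the last patient's last visit for February 2025, so on that timetable a note would come after data collection.

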4.2.4 Full Analysis set (FAS)

The FAS population will consist of all randomized patients who received at least one dose of the investigational product. FAS population will be analyzed according to intention-to-treat (ITT) principle, i.e., by treatment allocation regardless happening of intercurrent events. The FAS population will be used for the supplementary analyses of the primary analysis of the study and to present results on secondary efficacy data.

4.2.5 Safety set (SAF)

Standard/Forms/Template				
Title		Statistical Analysis Plan Template		
Code		Version	Effective Date	Page
PPD		01	29 Aug 2022	26 of 78

The SAF set will consist of all randomized patients who received at least one dose of the investigational product. SAF set will be analyzed according to the actual treatment received. The SAF population will be used to present results on safety data. For the derivation of the actual treatment, the longest exposure to the randomized/actual treatment will be considered: subjects will be analyzed using the actual treatment if they are exposed to it for the longest period of time (in case the exposure to the randomized treatment is equal to the exposure to the actual treatment, the actual treatment will be considered). The following scenarios will be considered:

- For patients with no issue with the randomized treatment, the actual will be equal to the randomized one
- For patients with issues (i.e., misallocation of the randomized treatment) the actual treatment will be derived by considering the longest exposure to the randomized/wrong treatment assigned: subjects will be analyzed using the treatment in the wrong kit assigned if they are exposed to it for the longest period of time (in case the exposure to the randomized treatment is equal to the exposure to the treatment in the wrong kit assigned, the “wrong” treatment will be considered).

Note: by chance, the misallocated kit could contain the treatment the patient had been randomized at.

4.2.6 Per Protocol set (PP)

The PP set will consist of all patients in the FAS population who do not have Protocol Deviations impacting on the analysis of primary endpoints (that lead to exclusion from PP set). The PP population will be used for supplementary analyses.

4.3 Usage of analysis sets

The usage of the analysis sets for the creation of tables and figures is illustrated in Table 2. Unless otherwise specified, all listings will be done for RND set. All listings will report:

- planned and actual treatment names included,
- the flag(s) of the analysis set(s) used to analyze the information of the listing (according to Table 2).

Table 2: Usage of Analysis Sets

Analysis	Screened Set	ENR	RND	FAS	SAF	PP
Subject enrolment and disposition	X	X	X			
Protocol deviations			X			
Study discontinuations			X			

Standard/Forms/Template						
Title		Statistical Analysis Plan Template				
Code		Version	Effective Date		Page	
PPD		01		29 Aug 2022		27 of 78

Analysis	Screened Set	ENR	RND	FAS	SAF	PP
IMP Discontinuations (for DMC, as described in section 4.9)					X	
Demographics and baseline characteristics			X*			
Medical/Surgical History and Concomitant Diseases			X			
Prior and concomitant medications		X			X	
Other baseline characteristics		X				
Compliance to IMP				X	X	
Exposure to IMP				X	X	
Analysis of primary efficacy endpoint		X				
Sensitivity analyses		X				
Supplementary analyses		X	X			X
Analysis of secondary efficacy endpoints				X		
Adverse events					X	
Clinical laboratory evaluation					X	
Vital signs					X	
ECGs					X	

* as described in section 4.9, additional analyses on demographics were requested by DMC and they were based on the RND set.

4.4 Estimands

4.4.1 Primary estimands

The primary estimand #1 is defined by the following attributes:

- Population: Adult patients hospitalized for Acute Respiratory Distress Syndrome, as defined by the inclusion-exclusion criteria of the study.
- Variables: Oxygenation index (OI) at baseline and at day 7.
- Intercurrent events:
 - Death before Day 7, or at Day 7 if OI is not present, as a terminal event which precludes the observation of the variable, will be handled by the composite strategy. Day 7 value is derived using Study Day based on Date (i.e., Day 7= First IMP Intake + 6), since only date of death is collected. The event will be included in the estimand by imputing for OI at day 7, an extreme unfavorable value characterizing the treatment failure. The 90°

Standard/Forms/Template				
Title		Statistical Analysis Plan Template		
Code		Version	Effective Date	Page
PPD		01	29 Aug 2022	28 of 78

percentile of the distribution of the observed values will be used (the value will be rounded to present only one decimal place only for data presentation, not for imputation).

- For patients that at day 7 are extubated and OI is not evaluable, extubation will be handled by the composite strategy as an event which precludes the observation of the variable of interest. The event will be included in the estimand by imputing for OI at day 7 a sufficiently extreme favorable value characterizing the treatment success. The 10° percentile of the distribution of the observed values will be used (the value will be rounded to present only one decimal place, only for data presentation, not for imputation). A patient is extubated at day 7 if the patient results not intubated in the time range [First IMP Intake Date/Time +132h, First IMP Intake Date/Time +155h and 59 min].
- Treatment discontinuation, which may affect interpretation of the variable, will be handled by the treatment policy strategy. The occurrence of the intercurrent event will be irrelevant. All observed values will be used regardless of occurrence of the intercurrent event. Retrieved dropouts will be used for data imputation of all missing data (not due to death and not due to extubation), whichever is the reason of missingness.
- Population-level summary: Change in oxygenation index (OI) from baseline to day 7

Estimand #1: Difference in means between Reparixin and Placebo in the change in oxygenation index (OI) from baseline to Day 7 in adult patients hospitalized for Acute Respiratory Distress Syndrome, as defined by the inclusion-exclusion criteria of the study, regardless of treatment discontinuation whatever the reason and alive up to day 7, intubated at Day 7.

The primary estimand #2 is defined by the following:

- Population: Adult patients hospitalized for Acute Respiratory Distress Syndrome, as defined by the inclusion-exclusion criteria of the study.
- Variables: Ventilator free days (VFD) at day 28.
- Intercurrent events:
 - Death before or on Day 28, as a terminal event which precludes the complete observation of the variable, will be handled by the composite strategy. The event will be included in the estimand with an extreme unfavorable value (0) characterizing the treatment failure.
 - Treatment discontinuation, which may affect interpretation of the variable, will be handled by the treatment policy strategy. The occurrence of the intercurrent event will be irrelevant. All observed values will be used regardless of occurrence of the

Standard/Forms/Template				
Title		Statistical Analysis Plan Template		
Code		Version	Effective Date	Page
PPD		01	29 Aug 2022	29 of 78

intercurrent event. Retrieved dropouts will be used for data imputation of all missing data (not due to death), whichever is the reason of missingness.

- Population-level summary: Mean VFD at day 28.

Estimand #2: Difference in means between Reparixin and Placebo in Ventilation Free Days (VFD) at Day 28 in adult patients hospitalized for Acute Respiratory Distress Syndrome, as defined by the inclusion-exclusion criteria of the study, regardless of treatment discontinuation whatever the reason and alive at day 28.

